9.5 Medical and Neurological History

Subject Samples:	Tables	Safety sample
	Listings	All subjects consented
	Figures	Not applicable

Subgroups: Not applicable
Abbreviation: MH

Standard Presentations

Medical history findings collected on the Medical History and Neurological History CRFs during the Initial Screening Period will be combined and summarized as follows:

MHT001 The number of subjects with at least one medical or neurological history finding will be presented by default summary statistics, where the percentage of subjects is calculated relative to the total number of subjects considered valid for the specific subject sample, for example, Safety subject sample. In addition, the number of subjects with at least one medical or neurological history finding within each primary SOC and PT, will be presented.

Standard subject data listings include:

MHL001 Medical and neurological history findings will be presented by-subject and within-subject by ascending order of start date of each medical history.

MHL002 A listing of the relevant MedDRA coding information, sorted in the same way as MHL001 will also be provided.

Study Specific Presentations

Not applicable.

9.6 Concomitant Medication

Concomitant medication will be presented as the number and percentage of subjects taking concomitant medication according to WHO-DD, 01 March 2011, primary ATC third level subgroup and generic name (corresponds to the first 6 digits of the 11-digit WHO-DD code). For the standard presentation, percentages will be calculated relative to the number of subjects considered valid for the Safety sample.

Subject Samples:	Tables	Safety sample and US Subset
	Listings	All subjects consented
	Figures	Not applicable
Subgroups:		Not applicable
Abbreviation:		CM

Standard Presentations

Concomitant medication assigned to the Treatment Period will be summarized as follows:

- CMT001 The number of subjects with at least one concomitant medication use in the Treatment Period will be presented by default summary statistics, where the percentage of subjects is calculated relative to the total number of subjects considered valid for the specific subject sample, that is, Safety subject sample. In addition, the number of subjects with at least one concomitant medication use within each ATC third level subgroup and generic name will be presented. The ATC third level subgroups are to be ordered alphabetically/numerically by ATC code and within ATC third level subgroup alphabetically by generic name.

All medications entered on the "Concomitant Medication" CRF form will be presented in subject data listings as follows:

- CML001 By-subject and within-subject by ascending start date/relative start day of medication use. In CML001 the relative start and stop day of concomitant medication use will be calculated relative to the start of the first infusion and will be presented for those subjects who were allocated to treatment and received at least one dose of investigational study medication. If the concomitant medication is "Ongoing" it will be indicated as such in the listing and the relative stop day will not be calculated. Only original dates will be presented in the listing even though the relative day may be based on an imputed date.
- CML002 A listing of the relevant WHO-DD coding information, sorted in the same way as CML001 will also be provided.

Study Specific Presentations

CMT002 The number of subjects with at least one anti-parkinsonian concomitant medication used in the Treatment Period will be presented by time interval (Year 1, Year 2, Year 3, Year 4, Year 5, > Year 5) using default summary statistics, where the percentage of subjects is calculated relative to the total number of subjects considered valid for the specific subject sample, that is, Safety Sample during the given time interval. In addition, the number of subjects with at least one concomitant medication use within each ATC third level subgroup and generic name will be presented. The ATC third level subgroups are to be ordered alphabetically/numerically by ATC code and within ATC third level subgroup alphabetically by generic name.

9.7 Drug Accountability

Subject Samples:	Tables	Not applicable
	Listings	All subjects consented
	Figures	Not applicable
Subgroups:		Not applicable
Abbreviation:		DA

Standard Presentations

Not applicable.

Study Specific Presentations

The following subject data listings will be prepared:

DAL001 The number of medication cassettes dispensed and returned will be presented.

9.8 Treatment Exposure

Subject Samples:	Tables	Safety sample and US Subset
	Listings	All subjects consented
	Figures	Not applicable
Subgroups:		First LCIG infusion study (3001/3002, 3003 or 3004)
Abbreviation:		EX

Standard Presentations

Not applicable.

Study Specific Presentations

- EXT001 The duration of 3005 LCIG exposure, overall duration of LCIG exposure, duration of 3005 PEG-J exposure, and overall duration of PEG-J exposure will be summarized using the same table format. These durations are defined in Section 6.4.1 (General Definitions) and also Section 8.3.2 and will be summarized using the appropriate default summary statistics. The number of subjects exposed will be presented by yearly time intervals (Year 1, Year 2, Year 3, Year 4, Year 5, > Year 5). A subject will be counted within an interval if their duration of exposure extended into the interval for 1 or more days. The total subject-years of exposure will also be presented.
- EXT002 The prescribed pump settings for the morning dose and flow rate at the conclusion of the preceding study will be summarized using the appropriate default summary statistics. The summary will not include subjects who enrolled in Study 3005 after completing Study 3003 because the prescribed pump settings were not recorded in that study.

EXT003 The average total daily levodopa dose at the final 3005 visit will be summarized with descriptive statistics for each component as well as for the total levodopa dose. Each subject's total daily levodopa dose at the end of titration in their initial LCIG study (Studies 3001, 3002, 3003 or 3004) will be retrieved from the relevant database. The total daily levodopa dose at the end of initial titration and the change from the end of initial titration to final 3005 visit will be summarized with descriptive statistics.

EXT004 The total daily levodopa dose at the end of initial titration and the change from the end of initial titration to final 3005 visit will be summarized by subgroup for the Safety Sample – US Subset.

Subject data listings include:

EXL001 A listing of treatment exposure data, including the first and last dates of 3005 LCIG infusion will be presented by-subject.

9.9 Efficacy Analyses

Subject Samples:	Tables	Efficacy Sample and US Subset
	Listings	All subject consented
	Figures	Not applicable
Subgroups:		First LCIG infusion study (3001/3002, 3003 or 3004), troublesome dyskinesia at initial LCIG infusion (< 1 hour, > 1 hour), dose of levodopa at initial LCIG infusion (< 1250 mg/day, > 1250 mg/day), and levodopa monotherapy during Study 3005 (yes, no)
Abbreviation:		QS

Standard Presentations

QST001 The average daily normalized "off" time will be summarized at initial LCIG infusion, at 3005 baseline and at 3005 endpoint as well as the change from initial LCIG infusion to 3005 endpoint and the change from 3005 baseline to 3005 endpoint. Descriptive statistics (including n, mean, minimum, maximum and 95% confidence interval) will be calculated.

Statistical tests for within group changes from initial LCIG infusion and from 3005 baseline will be implemented using PROC UNIVARIATE.

For the UNIVARIATE the following SAS[®] code will be used:

*PROC UNIVARIATE data = <SAS[®]-dataset> cibasic alpha = 0.05;
VAR OFFTIME;*

RUN;

The same methods defined above for average daily normalized "off" time will also be used to analyze the following assessments:

1. Change in average daily normalized "on" time without troublesome dyskinesia
2. Change in average daily normalized "on" time with troublesome dyskinesia
3. Change in average daily normalized "on" time with non-troublesome dyskinesia
4. Change in average daily normalized "on" time without dyskinesia
5. Change in the UPDRS total score, subscores of Parts I – IV and Part IV Questions 32, 33 and 34 (Dyskinesia items)
6. Change in the PDQ-39 summary index and each domain score

Variables derived from the PD Diary and PDQ-39 will be summarized for the Efficacy sample and the US subset of the Efficacy sample.

Variables derived from the UPDRS will be summarized for the US subset of the Efficacy sample.

QST002 The change from initial LCIG infusion to 3005 endpoint and from 3005 baseline to 3005 endpoint will be summarized by subgroup in the Efficacy sample – US Subset for the PD Diary variables.

QST003 The CGI score at 3005 endpoint will be summarized using the appropriate default summary statistics for the Efficacy sample.

Subject data listings will include:

- QSL001 A listing of Parkinson's Disease Diary data by-subject and within-subject by visit will be presented.
- QSL002 A listing of CGI-I scores by-subject and within-subject by visit will be presented.
- QSL003 A listing of PDQ-39 responses by subject and within-subject by visit will be presented.
- QSL004 A listing of UPDRS responses by subject and within-subject by visit will be presented.

9.10 Pharmacokinetic and Pharmacodynamic Analyses

No pharmacokinetic or pharmacodynamic analyses will be completed.

9.11 Analysis of Safety

9.11.1 Adverse Events

Adverse events (AEs) will be reported on a per-subject basis. This implies that even if a subject reported the same event repeatedly (same event that maps to the same PT), the event will be counted only once. In the latter case, the event will be assigned the worst severity and strongest relationship to the investigational study medication. Except for summaries of prevalence, the presentation of AEs is therefore restricted to the incidence per subject of AEs assigned to the Treatment Period. For summaries of prevalence over time, each event (all events that map to the same PT) will be counted only once per subject for each time period presented.

Subject Samples:	Tables	Safety sample and US subset of safety sample
	Listings	All subjects consented
	Figures	Not applicable
Subgroups:		Gender, age category (< 65, ≥ 65), duration of Parkinson's disease (< 10 years, ≥ 10 years), country
Abbreviation:		AE

Standard Presentations

Adverse events will be summarized by default summary statistics, for all centers/countries combined as well as for subjects enrolled at US sites. Percentages will be calculated relative to the total number of subjects considered valid for the subject sample.

The following standard presentations will be produced for all TEAEs in the Safety subject sample.

- AET001 Overview of AEs including the number of subjects with:
- At least one TEAE.
 - At least one TEAE that is at least possibly drug-related.
 - At least one serious TEAE.
 - At least one SAE.
 - Any AE leading to death.
 - A TEAE leading to death.
 - A TEAE leading to premature discontinuation.
 - At least one severe TEAE.
- AET002 Incidence of TEAEs will be presented by primary SOC and PT. The primary SOCs are to be ordered alphabetically. Within each SOC, the PT is also to be ordered alphabetically.
- AET003 Incidence of TEAEs will be presented by PT. SOCs will not be presented and PTs will be ordered by decreasing frequency of occurrence.

- AET004 Incidence of TESAEs will be presented by primary SOC and PT. The primary SOCs are to be ordered alphabetically. Within each SOC, the PT is also to be ordered alphabetically.
- AET005 Incidence of TEAEs leading to premature discontinuation will be presented by primary SOC and PT. The primary SOCs are to be ordered alphabetically. Within each SOC, the PT is also to be ordered alphabetically.
- AET006 For each defined category of special interest, incidence of TEAEs will be presented by primary SOC and PT. The primary SOCs are to be ordered alphabetically. Within each SOC, the PT is also to be ordered alphabetically.
- AET007 Incidence of TEAEs by strongest relationship. A default frequency table by primary SOC and PT will be presented. The primary SOCs are to be ordered alphabetically. Within each SOC, the PT is also to be ordered alphabetically.
- AET008 Incidence of TEAEs that are at least possibly related to treatment will be presented by primary SOC and PT. The primary SOCs are to be ordered alphabetically. Within each SOC, the PT is also to be ordered alphabetically.
- AET009 Incidence of TEAEs by maximum severity. A default frequency table by primary SOC and PT will be presented. The primary SOCs are to be ordered alphabetically. Within each SOC, the PT is also to be ordered alphabetically.

In addition, AE data will be listed as follows:

- AEL001 All AEs by-subject and within-subject by start date/relative start day of the adverse event. In AEL001 the relative start and stop day of the AE will be calculated relative to the date of the first 3005 LCIG infusion and will be presented for the Safety subject sample. If the AE is "Ongoing" it will be indicated as such in the listing and the relative stop day will not be calculated. Only original dates will be presented in the listing even though the relative day may be based on an imputed date.
- AEL002 A listing of the relevant MedDRA coding information will be provided as AEL002, sorted in the same chronological order as AEL001.

- AEL003 Listing of deaths. AEL003 also includes the general demographic data for each subject who died (gender, age, ethnicity and race).
- AEL004 Listing of SAEs. AEL004 lists all subjects with at least one serious adverse event indicating whether the SAE is treatment-emergent or not.
- AEL005 Listing of TEAEs leading to study termination. AEL005 will be presented for those subjects valid for the Safety subject sample with at least one adverse event for which the question "Led to Study Termination" is indicated as "Yes."
- AEL006 Listing of TEAEs of special interest. A listing will be presented for each AE of special interest category.

Study Specific Presentations

- AET010 Incidence of TEAEs that have been linked to a device complication by investigators through the Device Complication CRF. A default frequency table by primary SOC and PT will be presented. The primary SOC's are to be ordered alphabetically. Within each SOC, the PT is also to be ordered alphabetically.
- AET011 Incidence of TEAEs within each consecutive 3005 Treatment Year (as defined in Section 6.4.9) will be summarized. A default frequency table by primary SOC and PT will be presented. The primary SOC's are to be ordered alphabetically. Within each SOC, the PT is also to be ordered alphabetically.
- AET012 Incidence of TEAEs within subgroups. A default frequency table by primary SOC and PT will be presented for each subgroup category. The primary SOC's are to be ordered alphabetically. Within each SOC, the PT is also to be ordered alphabetically.
- AET013 Incidence of TEAEs with a fatal outcome will be presented by primary SOC and PT. The primary SOC's are to be ordered alphabetically. Within each SOC, the PT is also to be ordered alphabetically.
- AET014 Prevalence of TEAEs within each consecutive 3005 Treatment Year (as defined in Section 6.4.9) will be summarized. A default frequency table by primary SOC and PT will be presented. The primary SOC's are to be ordered alphabetically. Within each SOC, the PT is also to be ordered alphabetically.

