The final visit in the previous open-label LCIG study will provide baseline assessments for the S1878.3.005 study. Subjects will be reassessed every 6 months for the appropriateness of the continuation of treatment with LCIG. If the subject is deemed inappropriate for continued treatment by the Investigator, the subject would be discontinued from treatment and the PEG-J will be removed, with a follow-up visit

occurring 1 week later. For subjects who elect not to continue LCIG treatment, the PEG-J will be removed, and a follow-up clinic visit will occur 1 week later.

Safety assessments should include physical examination, neurological exam, orthostatic vital signs, weight, adverse event monitoring, assessment of impulsive behavior and sleep attacks, melanoma check, electrocardiogram (ECG), clinical hematology, biochemistry, special labs to monitor for vitamin deficiencies, and urinalysis.

The following efficacy assessments will be completed at US sites:

- Parkinson's Disease Diary[®] assessment of motor state completed for the 3 consecutive days prior to each clinic visit (excluding the drug dispensation visits),
- Unified Parkinson's Disease Rating Scale (UPDRS), and
- Parkinson's Disease Questionnaire-39 (PDQ-39).

At each visit, complications or adverse events with the infusion device (i.e., the tubing system and the pump) will also be recorded and reported. Tube placement will be checked by radiography if there is a clinical indication that the tube has been displaced. The tube will be repositioned, if needed, to the original placement site just beyond the ligament of Treitz. At each visit the tube insertion site, including the stoma, will also be inspected. On a yearly basis, at a minimum, an assessment will be made of the need for a replacement of the PEG-J. The frequency of replacement should be in accordance with local practice.

The protocol duration is planned until the finished product is available commercially in the respective countries where subjects are participating in the study. The expected protocol duration will continue through successful NDA and subsequent approval (approximately 4 years). ***The protocol duration will be extended 4 years in the UK from the approval date of Amendment 3.01. If it is deemed necessary to continue treatment after 4 years in the UK, either an amendment to the current protocol will be made or a new protocol will be submitted.***

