6.4 Day Numbers, Study Periods and Visit Windows: Related Definitions

6.4.1 General Definitions

Assessment days will be related to the date of the first infusion of 3005 study drug (First 3005 LCIG Infusion). Baseline is defined in Section [6.4.5](#) (Baseline Period). The Cutoff Date for the 2015 interim analysis will be 30 September 2015. Assessments and/or measurements performed after the Cutoff Date, adverse events or device complications with start dates after the Cutoff Date, and concomitant medications with start dates after

the Cutoff Date will not be included in the 2015 interim analysis. No cutoff date will be applied to the analysis for the final CSR.

The following reference dates will be defined for all subjects in the All Subjects Consented subject sample defined in Section 8.1.1.

- **Date of the First 3005 LCIG Infusion (Day 1, RFSTDTN):**

The actual dates of study drug administration are not recorded in the 3005 database. The dates when 3005 study drug is dispensed are recorded in the DA raw data panel. For analysis, the date of the first 3005 LCIG infusion will be defined as the first date that 3005 study drug was dispensed to the subject. The visit date recorded in the DM raw data panel will be used if the date the first study drug was dispensed is not available.

The date of the first 3005 LCIG infusion will be defined as Day 1 and is the key variable RFSTDTN and is used in the calculation of relative days.

- **Date of the Last 3005 LCIG Infusion (RFENDTN):**

For subjects who have prematurely discontinued or completed the study, the date of the last 3005 LCIG infusion will be the earliest of 1) the date of last study drug administration collected on the DS raw data panel, 2) the date of discontinuation or study completion collected on the DS raw data panel and 3) the Cutoff Date (interim analysis only).

For the 2015 interim analysis, the date of the last 3005 LCIG infusion for all ongoing subjects will be the Cutoff Date.

- **Duration of 3005 LCIG Infusion (LDA):**

The Duration of 3005 LCIG Infusion or exposure to treatment is equal to the day number of the Last 3005 LCIG Infusion (LDA) and is derived as follows from the previous two dates:

$$\text{LDA (days)} = (\text{Date of the Last 3005 LCIG Infusion [RFENDTN]} - \text{Date of the First 3005 LCIG Infusion [RFSTDTN]}) + 1$$

LDA then indicates the relative day of the last 3005 LCIG infusion for each subject.

- **Date of Last 3005 PEG-J Exposure (RFENDT2N):**

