8.1.5 Subject Enrollment and Disposition

As previously described, Study 3005 is an extension study. Subjects will be assigned to an enrollment cohort based on the study in which they received their first LCIG infusion. Due to the similarity in study design, Study 3001 and Study 3002 will be considered a single enrollment cohort. The number and percentage of subjects in each of the following enrollment cohorts will be summarized:

- Subjects who received their first LCIG infusion in Study S187.3.001 or Study S187.3.002
- Subjects who received their first LCIG infusion in Study S187.3.003
- Subjects who received their first LCIG infusion in Study S187.3.004

Subjects are expected to continue in the study until commercial LCIG becomes available to them. If commercial LCIG becomes available to a subject, a final visit shall be scheduled and the subject will be regarded as having completed the study if they complete this final visit. If at any time after providing informed consent, a subject prematurely discontinues their participation in the study, the primary reason for premature discontinuation shall be recorded on the "Study Termination" CRF. The primary reason can include one of the following:

- Adverse Event
- Lack of Efficacy
- Lost to Follow-up
- Withdrew Consent
- Administrative
- Protocol Violation

Premature discontinuations will be summarized by 3005 treatment year after allocating each premature discontinuation to a 3005 treatment year based on the study day of the subject's last dose date and the study day intervals described in Section 6.4.9.

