8.3.2 Duration of Study Drug and PEG-J Exposure

The duration of LCIG exposure as well as the duration of PEG-J exposure will be summarized for 3005 as well as overall. The duration of 3005 LCIG infusion (LDA) is described in detail in Section 6.4.1 (General Definitions). The duration of 3005 PEG-J exposure will be calculated as the Date of the Last 3005 PEG-J Exposure (as defined in Section 6.4.1) – the Date of the First 3005 LCIG Infusion (as defined in Section 6.4.1) +1. The total subject-years of exposure will be calculated as the sum of all subject exposures in days divided by 365.25.

As previously described, Study 3005 is an extension of the previous Studies 3001, 3002, 3003, and 3004. To determine the overall duration of each subject's LCIG and PEG-J exposure, the date of initial PEG-J placement and the date of initial LCIG infusion will be retrieved from the relevant study database. The overall duration of LCIG infusion will be

calculated as the Date of the Last 3005 LCIG Infusion – the Date of the Initial LCIG Infusion +1. The overall duration of PEG-J exposure will be calculated as the Date of Last 3005 PEG-J Exposure – the Date of the Initial PEG-J placement +1.

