The percentage of each of the aforementioned AE types will be determined as the number of subjects with at least one mention of the AE type relative to the number of subjects at risk. A subject will be considered at risk if the subject is in the Safety subject sample.

In addition to the aforementioned AE types, AEs reported by the Investigator as related to device complications will also be summarized. Device complications are captured in the DE raw data panel and associated AEs are captured in the AE raw data panel.

Investigators link the AEs that are related to device complications by entering an AE number in the DE raw data panel.

The incidence and prevalence of TEAEs during each 3005 Treatment Year will be summarized using the study day intervals described in Section 6.4.9. AE start days and Treatment Period end days will be calculated relative to the start of 3005 LCIG infusion (RFSTDTN) as follows:

$$\text{AE Start Day} = (\text{AE Start Date} - \text{Date of First 3005 LCIG Infusion}) + 1$$

$$\text{Treatment Period End Day} = ([\text{Date of Last 3005 PEG-J Exposure} + 30 \text{ Days}] - \text{First Date of 3005 LCIG Infusion}) + 1$$

For summaries of incidence, the count (and numerator for percentage calculations) will be the number of subjects who had their first treatment-emergent occurrence of the PT start

within the study day range for the 3005 Treatment Year. Each subject will be counted at most once within each SOC and PT.

For summaries of prevalence, the count (and numerator for percentage calculations) will be the number of subjects who had a treatment-emergent occurrence of the PT start within the study day range for the 3005 Treatment Year or who had an earlier treatment-emergent occurrence of the PT that had not ended prior to the start of the study day range for the 3005 Treatment Year.

The denominator for both incidence and prevalence percentage calculations will include all subjects whose Treatment Period End Day is within or greater than the study day range for the 3005 Treatment Year.

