SAP Table Code	Table Number	Table Title
AET006	14.3__1.2.2.13	Number and Percent of Subjects with Treatment-Emergent Adverse Events of Special Interest Related to Polyneuropathy and Associated Signs and Symptoms (Narrow Search) SAFETY SAMPLE
AET006	14.3__1.2.2.14	Number and Percent of Subjects with Treatment-Emergent Adverse Events of Special Interest Related to Weight Loss SAFETY SAMPLE
AET006	14.3__1.2.2.15	Number and Percent of Subjects with Treatment-Emergent Adverse Events of Special Interest Related to Cardiovascular Fatalities SAFETY SAMPLE
AET006	14.3__1.2.2.16	Number and Percent of Subjects with Treatment-Emergent Adverse Events of Special Interest Related to Aspiration SAFETY SAMPLE
AET012	14.3__1.2.3.1	Number and Percent of Subjects with Treatment-Emergent Adverse Events Subgroup: Gender SAFETY SAMPLE
AET012	14.3__1.2.3.2	Number and Percent of Subjects with Treatment-Emergent Adverse Events Subgroup: Age Category SAFETY SAMPLE
AET012	14.3__1.2.3.3	Number and Percent of Subjects with Treatment-Emergent Adverse Events Subgroup: Duration of Parkinson's Disease SAFETY SAMPLE
AET012	14.3__1.2.3.4	Number and Percent of Subjects with Treatment-Emergent Adverse Events Subgroup: Country SAFETY SAMPLE
AET001	14.3__1.2.4.1	Summary of Adverse Events SAFETY SAMPLE – US SUBSET
AET002	14.3__1.2.4.2	Number and Percent of Subjects with Treatment-Emergent Adverse Events SAFETY SAMPLE – US SUBSET
AET013	14.3__1.2.4.3	Number and Percent of Subjects with Treatment-Emergent Adverse Events with Fatal Outcome SAFETY SAMPLE – US SUBSET
AET004	14.3__1.2.4.4	Number and Percent of Subjects with Treatment-Emergent Serious Adverse Events SAFETY SAMPLE – US SUBSET
AET005	14.3__1.2.4.5	Number and Percent of Subjects with Treatment-Emergent Adverse Events Leading to Study Termination SAFETY SAMPLE – US SUBSET
AET006	14.3__1.2.4.6	Number and Percent of Subjects with Treatment-Emergent Adverse Events of Special Interest Related to Procedure and Device SAFETY SAMPLE – US SUBSET
AET006	14.3__1.2.4.7	Number and Percent of Subjects with Treatment-Emergent Adverse Events Not Related to Procedure and Device SAFETY SAMPLE – US SUBSET

SAP Table Code	Table Number	Table Title
AET006	14.3__1.2.4.8	Number and Percent of Subjects with Treatment-Emergent Adverse Events of Special Interest Related to Polyneuropathy and Associated Signs and Symptoms SAFETY SAMPLE – US SUBSET

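### The main, US-subset and by-country adverse-event tables give crude percentages although follow-up is open-ended and tied to each country's launch, so they need exposure-adjusted rates beside them

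*SAP*

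**What the plan says.** Protocol 13.1 makes long-term safety the primary statistical objective. Four parts of the plan bear on how adverse events are counted.

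- **Denominator.** SAP 9.11.1: "Percentages will be calculated relative to the total number of subjects considered valid for the subject sample". SAP 8.5.1 adds: "A subject will be considered at risk if the subject is in the Safety subject sample". Time on study plays no part in either rule.
- **Length of follow-up.** Protocol 7.1: "The protocol duration is planned until the finished product is available commercially in the respective countries where subjects are participating in the study". SAP 8.1.5: "Subjects are expected to continue in the study until commercial LCIG becomes available to them". Protocol 7.1 also has a rule for one country: "The protocol duration will be extended 4 years in the UK from the approval date of Amendment 3.01". SAP 6.4.1 fixes the interim cut: "For the 2015 interim analysis, the date of the last 3005 LCIG infusion for all ongoing subjects will be the Cutoff Date". Visit labels in SAP 6.3 run to Month 84.
- **Tables by country and for the US.** SAP 12.2 lists AET012 as "Number and Percent of Subjects with Treatment-Emergent Adverse Events Subgroup: Country SAFETY SAMPLE", and US-subset versions of AET001, AET002, AET004 and AET006. All are numbers and percentages of subjects.
- **Where exposure does enter.** SAP 8.3.2: "The total subject-years of exposure will be calculated as the sum of all subject exposures in days divided by 365.25". This goes into EXT001, for the Safety sample and the US subset. SAP 8.5.1 also defines incidence (AET011) and prevalence (AET014) by 3005 Treatment Year, with denominators limited to subjects whose treatment period reaches that year.

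No exposure-adjusted adverse-event rate and no time-to-event summary is planned.

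**The concern.** A subject followed for a few months counts in the denominator exactly as one followed for six years. That would matter less if follow-up were similar everywhere, but here it is set by the date of local launch, which is a property of the country. Readers will put the columns of AET012 side by side, and will set the US-subset tables against the overall ones. A difference may then reflect how long subjects stayed rather than how often events occurred, and a real difference in rate may be hidden or reversed.

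The companion tables do not close the gap where it is widest. By country there is neither a by-year table nor an exposure table. For the US subset there is exposure but no by-year table. Even in the full Safety sample, serious TEAEs, polyneuropathy, weight loss, cardiovascular fatalities and aspiration have crude percentages only.

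**Working it through.** **No figure to reproduce.** The documents state no adverse-event rate, launch date or follow-up by country, and Protocol 13.4 gives alpha as not applicable. All hazards and durations below are assumptions, shown as a range.

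**Step 1: which tables take account of time.** From SAP 12.2:

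| Tables | By-year version | Subject-years in EXT001 |
|---|---|---|
| All TEAEs, Safety sample | Yes | Yes |
| Procedure/device events, Safety sample | Yes | Yes |
| Events not procedure/device, Safety sample | Yes | Yes |
| Serious TEAEs and other AESIs, Safety sample | No | Yes |
| US subset | No | Yes |
| By country (AET012) | No | No |

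**Step 2: crude percentage at a fixed rate.** With constant hazard r per year and follow-up of T years, the expected percentage with at least one event is 100 × (1 − exp(−rT)).

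| r | 1 year | 2 years | 4 years | 5 years |
|---|---|---|---|---|
| 0.05 | 4.9% | 9.5% | 18.1% | 22.1% |
| 0.10 | 9.5% | 18.1% | 33.0% | 39.3% |
| 0.20 | 18.1% | 33.0% | 55.1% | 63.2% |

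Each row has a single underlying rate. The order of two countries can reverse: 0.05 per year followed for 5 years shows 22.1%, while 0.10 per year followed for 1 year shows 9.5%. If follow-up differs little, so do the percentages: at 0.10 per year, 3 against 4 years gives 25.9% against 33.0%.

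**Step 3: what a first-event rate gives.** Expected time at risk per subject, to first event or end of follow-up, is (1 − exp(−rT))/r. Dividing the expected proportion with an event by this returns r. At r = 0.10 the result is 10.0 per 100 subject-years whether T is 1, 2 or 5. Dividing by the total subject-years of EXT001 is only approximate, because time after the first event stays in the denominator: 9.5/1 = 9.5, 18.1/2 = 9.1 and 39.3/5 = 7.9 per 100 subject-years.

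**Step 4: AET011 as written.** The numerator counts subjects whose first occurrence of a term falls in the year. The denominator is everyone whose treatment period reaches that year, including those who already had the event. With no dropout, the expected entry for year y is 100 × (exp(−r(y−1)) − exp(−ry)). At a constant r = 0.20:

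| Year | 1 | 2 | 3 | 4 | 5 |
|---|---|---|---|---|---|
| AET011 as written | 18.1% | 14.8% | 12.2% | 9.9% | 8.1% |
| Among subjects still without the event | 18.1% | 18.1% | 18.1% | 18.1% | 18.1% |

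A constant first-event rate would look like a falling one. The rule also counts a subject who leaves part-way through a year as a whole subject for that year.

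**The case against.** - **The plan does not disregard follow-up.** A reader might infer from the denominator rule that it does. The documents do not support that: AET011 and AET014 have denominators that shrink as subjects leave, procedure/device events have their own by-year incidence and prevalence tables, and EXT001 gives duration, numbers exposed by year and subject-years. This stands and limits the point to the tables named above.
- **No comparison is planned.** The study has a single arm, SAP 8.1.2 calls the safety subgroups exploratory, and no test between countries is specified. The US subset is part of the overall sample and is defined to describe those subjects. A reader might conclude that the country percentages are wrong or meaningless. They are neither: each is a valid count of subjects with an event over the follow-up that occurred. What they lack is the exposure needed to compare them.
- **The size is unknown.** This is correct. Month 84 is the last visit label and is not evidence that countries differ widely. If launches were close together, the distortion would be modest.
- **Nothing is lost.** Listings hold infusion dates, adverse-event start days and demographics including country, so rates could be added later. This is true, but it also means the change can be specified now without new data.
- **AET011 already checks for a constant rate.** It is tempting to rely on the by-year table for this. Step 4 shows that, as written, it cannot serve that purpose.

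**Conclusion.** The point holds in limited form. The main, US-subset and by-country tables (AET001, AET002, AET004, AET006, AET012) report crude percentages in a study whose follow-up depends on country by design. Across countries or subsets those percentages are not comparable without exposure adjustment, and for countries the plan does not give the exposure with which to adjust them.

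The figures are illustrations that rest on assumed constant hazards and equal follow-up within each group. They show what a given difference in follow-up would do, not that such a difference occurred. The AET011 result assumes no dropout, but its cause (subjects with an earlier event kept in the denominator) is in the SAP's own definition.

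The case for acting is that long-term safety is the primary statistical objective and the dates required are already derived. Label: Cheap improvement.

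**What to change.** 1. Beside the percentages in the treatment-emergent rows of AET001, and in AET002, AET004, AET006 and AET012 and the US-subset versions that are listed, add the number of subjects with a first event per 100 subject-years at risk, with 95% CI. Time at risk runs from the first 3005 infusion to the first event or the end of the TEAE window (last PEG-J exposure plus 30 days), whichever is earlier.
2. Add duration and subject-years by country to EXT001.
3. In AET011, remove from each year's incidence denominator subjects with an earlier treatment-emergent event of the same term. Part-years would still count as whole years, which a footnote should say.

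**Cost.** No new data: AE Start Day and Treatment Period End Day are already defined in SAP 8.5.1. Person-time must be derived separately for each SOC and PT row, which is more than dividing by one total. Tables become longer. With about 275 subjects at about 70 centers, rates in small countries will be imprecise, and the CI will show it. A single rate also assumes a constant hazard, which AET011 as now written cannot check; change 3 makes it more useful for that, though only in the full Safety sample.
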